eCRF	Electronic Case Report Form
EWOC	Escalation with overdose control
FAS	Full analysis set
FIH	First in human
FSH	Follicle stimulating hormone

hCG	Human chorionic gonadotropin
HLA	Human leukocyte antigen
HLA-A*0201	Human leukocyte antigen-A*0201
HLA-DR	Human leukocyte antigen-DR
ICF	Informed consent form
ICH	International Conference on Harmonization
IL-#	Interleukin-# (e.g. IL-6, IL-10)
IPE	Intra-patient escalation
IRS	Integrated response system
IV	Intravenous
LAGE-1A	L antigen family member-1 isoform A
LAGE-1B	L antigen family member-1 isoform B
██████	██
MedDRA	Medical Dictionary for Regulatory Activities
██████	██
MTD	Maximum tolerated dose
N-CRM	N-Continual Reassessment Method
NCI	National Cancer Institute
NSCLC	Non-small cell lung cancer
NY-ESO-1	New York esophageal squamous cell carcinoma-1
ORR	Objective response rate
OS	Overall survival
PBMC	Peripheral blood mononuclear cell
PD	Progressive disease
PD-1	Programmed death-1
PD-L1	Programmed death-ligand 1
PFS	Progression-free survival
PK	Pharmacokinetic
PPS	Per protocol set
PR	Partial response
PT	Preferred Term

QTcF	QT interval corrected by Fredericia's method
QW	Every week
RECIST	Response Evaluation Criteria in Solid Tumors
RP2D	Recommended Phase 2 dose
SAE	Serious adverse event
SAF	Safety Analysis Set
SAP	Statistical Analysis Plan
SD	Stable disease
SOC	System Organ Class
SST	Study Safety Team
$t_{1/2}$	Terminal elimination half-life
T3	Triiodo thyroxine
T4	Thyroxine
TEAE	Treatment-emergent adverse events
TIL	Tumor infiltrating lymphocyte
T_{max}	Time of maximum concentration
████	████████████████████
TSH	Thyroid stimulating hormone
ULN	Upper limit of normal
US	United States
V_{ss}	Steady state volume of distribution
WBC	White Blood Cell
WHO	World Health Organization

1 Introduction

This statistical analysis plan (SAP) describes the analyses and data presentations for the clinical study protocol IMCnyeso-101 version 4.0, dated 24 Feb 2020. This study is a Phase I/II, open-label, multi-center trial. Phase I of the study is a dose escalation to determine the maximum tolerated dose (MTD) or recommended Phase II dose (RP2D) of IMCnyeso administered weekly as monotherapy in patients with advanced non-small cell lung cancer (NSCLC), melanoma, urothelial cancer and synovial sarcoma; Phase II of the study is expansion in three disease cohorts (NSCLC, urothelial cancer and synovial sarcoma patients).

Any differences between this SAP and protocol version 3.0 are documented in Section 12.

This SAP describes statistical analyses that will be produced in three deliveries:

1. Phase I Summary Report

Based on a cut-off of Phase I patients once MTD/RP2D has been determined and all patients having completed DLT evaluation.

2. Full Clinical Study Report (CSR) of Phase I and Phase II

Based on a cut-off at the time where at least 80% of phase II patients in each cohort have completed the follow up for disease progression or discontinued the study for any reason (once each cohort has reached this point, separate reporting will be considered for each cohort).

- There will be an interim analysis for each Phase II cohort (s). It will only involve BOR endpoint.

3. Follow-up Abbreviated CSR

Based on the locked database after 100% follow up of all patients from both phases.

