6.10.2 Definition of DLT-Evaluable Patients for the Dose-Determining Set

Patients are considered as DLT-evaluable if they meet one of the following criteria:

- Experienced a DLT during the 28-day DLT evaluation period, **OR**
- Did not experience a DLT during the 28-day DLT evaluation period, received at least 3 of the 4 planned doses of IMCnyeso (including at least 2 doses at the target dose level), and were observed for \geq 28 days following the first dose

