7.2 Treatment Period Schedule

The treatment period starts with Day 1 of Cycle 1 (C1D1). A treatment cycle is defined as 28 days for the purposes of scheduling procedures and evaluations.

Any assessments required on C1D1 that are also performed as part of Screening do not need to be repeated on C1D1 if the data were obtained 72 hours prior to the first dose of study treatment. For subsequent visits, pregnancy testing may be performed up to 72 hours prior to dosing and other safety assessments may be performed up to 24 hours prior to dosing.

During the study visits, all tests and/or procedures should occur on schedule whenever possible. A visit window of ± 7 days (with a minimum of 7 days between doses of IMCnyeso) is allowed unless otherwise indicated in the protocol. If study drug infusions are delayed, the assessments associated with those infusions should be rescheduled accordingly. However, the timing of protocol-specified radiological assessments should be calculated in weeks using C1D1 as reference and should not be adjusted because of delays in treatment.

Assessments required during the treatment period are presented by visit in [Table 7-2](#). For patients receiving IPE, follow the alternate Cycle 1 schedule provided in [Section 13.4](#). Assessments marked “X” should be performed prior to dosing. Assessments that are to be performed at multiple timepoints are marked with the number of timepoints (including optional timepoints, if applicable) for the visit (eg, 2 \times is twice) and details of the timepoints are provided in the footnote. Additional details regarding the assessments are provided in [Section 7.4](#). Please refer to [Section 6](#) for dosing details. Patients will continue treatment until they meet criteria for discontinuation, as described in [Section 6.16](#).

Table 7-2: Schedule of Treatment Period Assessments

Procedure	Cycle 1						Cycle 2				Cycle 3				Later Cycles			
Day of Cycle	1	2	8	9	15	22	1	8	15	22	1	8	15	22	Visits on Days 1, 8, 15, and 22			
Adverse events	X	X	X	X	X	X	X	X	X	X	X	X	X	X		X		
Concomitant medications	X	X	X	X	X	X	X	X	X	X	X	X	X	X		X		
Safety Assessments																		
Complete physical examination	X																	
Abbreviated physical examination			X		X	X	X	X	X	X	X	X	X	X		D1 of each cycle		
Weight	X						X				X						D1 of each cycle	
Vital signs	~14x	~14x		3x	3x	3x	3x	3x	3x	3x	3x	3x	3x	3x		3x each dosing day		
12-lead ECG (single)	2x						2x				2x					2x on C4D1, C5D1, and C6D1		

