ECOG performance status	X											X					D1 of each cycle	
Hematology panel	X	X	X	X	X	X	X	X	X	X	X		X				D1 of each cycle	
Chemistry panel	X		X		X	X	X	X	X	X	X		X				D1 of each cycle	
Thyroid function	X						X				X							
Urine pregnancy test (women of childbearing potential)	X						X				X						D1 of each cycle	
PK and Immunogenicity																		
Pharmacokinetic sampling	8x	3x	8x	X	4x	4x	2x		2x		2x		2x			2x on D1 of odd-numbered cycles		
Immunogenicity sampling	X		X		X		X				X						D1 of odd-numbered cycles	
Disease Assessment																		
CT/MRI scans and disease assessment												X				Q8W to W40 (C3, C5, C7, C9, C11), then Q12W (C14, C17, etc)		
Tumor biopsy	Between C1D9 and C1D16 (required for ≥ 10 patients in Phase II, optional for all other patients) Optional for all patients at time of progression																	

IMCnyeso administration	X		X		X	X	X	X	X	X	X	X	X	X	D1, D8, D15, and D22 of each cycle
-------------------------	---	--	---	--	---	---	---	---	---	---	---	---	---	---	------------------------------------

AE = adverse event; C#D# = Cycle # Day #; [REDACTED]; CT = computerized tomography; ECG = electrocardiogram; ECOG = Eastern Cooperative Oncology Group; EOI = end of infusion; hr = hour(s); min = minutes; MRI = magnetic resonance imaging; [REDACTED]; PK = pharmacokinetics; Q#W = every # weeks; [REDACTED]; W = week.

ECG assessments are to be done pre-dose and within 1 hour of EOI on indicated days.

Vital signs (body temperature, pulse, respiratory rate, and blood pressure; in addition, oxygen saturation should be collected for \geq first 3 cycles of treatment) are to be assessed at the following timepoints:

- C1D1/C1D2 and C1D8/C1D9: pre-dose (within 2 hours), EOI (within 15 min), every 2 hours (\pm 15 min) through 12-hour post-EOI, every 4 hours (\pm 30 min) until discharge
- All other doses: pre-dose (within 2 hours), EOI (within 15 min), and 1-hour post-EOI (\pm 15 min)

Pharmacokinetics samples are to be collected at the following timepoints:

- C1D1 and C1D8: pre-dose (within 2 hours), EOI (within 15 min), 1-hour post-EOI (\pm 15 min), 2-hour post-EOI (\pm 15 min), 4-hour post-EOI (\pm 15 min), 6-hour post-EOI (\pm 30 min), 8-hour post-EOI (\pm 1 hr), and 12-hour post-EOI (\pm 3 hr)
- C1D2: 24-hour post-EOI (\pm 4 hr), 36-hour post-EOI (optional, \pm 4 hr), and 48-hour post-EOI (optional, \pm 4 hr)
- C1D9: 24-hour post-EOI (\pm 4 hr)

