9 STATISTICAL METHODS AND DATA ANALYSES

9.1 General Principles

Categorical data will be presented as frequencies and percentages. For continuous data, the mean, standard deviation, median, minimum and the maximum will be presented.

The Phase I study data will be analyzed and reported based on all patient data from the dose escalation up to the time when all Phase I patients have completed at least 6 cycles of treatment or have discontinued study treatment. Data will be listed, summarized, and analyzed by treatment group. Data for the Phase II expansion cohorts will be reported separately, with a data cut off at the point where at least 80% of patients have completed the follow up for disease progression or discontinued the study for any reason. Additional details of data reporting will be outlined in the statistical analysis plan (SAP).

The following rules will be followed for reporting results unless stated otherwise:

- Screen failure patients are those who signed the ICF, but never started the study treatment for any reason. For these patients, the eCRF data collected will not be included in analyses, but will be reported in the clinical study report as separate listings
- Baseline is defined as the last assessment prior to the first dose of treatment received (ie, C1D1 pre-dose)
- For Phase I, all summaries, listings, figures and analyses will be performed by treatment group
- For Phase II, all summaries, listings and figures for primary efficacy analyses and safety analyses will be presented by disease group (NSCLC, urothelial carcinoma, or synovial sarcoma)

Patients from the dose escalation and dose expansion may be pooled for the RP2D. Additional analyses not described here will also be detailed in the SAP.

Unless otherwise stated, missing data will simply be noted as missing on appropriate tables/listings.

Compliance with the protocol will be assessed by the number and proportion of patients with protocol deviations. Protocol deviations will be identified prior to database lock and will be listed and summarized.

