10.3 Pharmacodynamics

Cytokines and lymphocytes are analyzed and are covered by this SAP. No other pharmacodynamics analysis would be performed.

11 Interim Analysis

No formal interim analysis is planned during Phase I. The BLRM will be updated after each dose-escalation cohort and the MTD / RP2D will be determined at the end of Phase I (see Section 3.1).

A formal interim analysis will be conducted during Phase II. ORR will be evaluated for the first 9 patients in each Phase II cohort to determine whether enrollment may continue (see Section 4.1).

12 Changes in the Planned Analysis

There were no substantial changes from the planned analyses described in the protocol version 4.0, dated 24 Feb 2020 to those presented in this SAP. The following minor detail has changed from the protocol:

- All Patients Set has been added to allow for additional disposition summaries to be conducted
- Safety RP2D Analysis Set has been added to allow for some analyses to be conducted on patients pooled across phases if they receive RP2D.

13 References

14 Appendices

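### SAP delivery 1 cuts Phase I data at the end of DLT evaluation, not at the protocol's 6 cycles; the change is undeclared and too early for response rates in recently enrolled patients

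*SAP*

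**What the plan says.** Two cuts are given for the Phase I report.

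- Protocol 9.1 analyses and reports Phase I on data "up to the time when all Phase I patients have completed at least 6 cycles of treatment or have discontinued study treatment".
- SAP Section 1 lists three deliveries. The first, the Phase I Summary Report, is "Based on a cut-off of Phase I patients once MTD/RP2D has been determined and all patients having completed DLT evaluation". The second is the full CSR of both phases, triggered by Phase II follow-up. The third follows complete follow-up of both phases. None uses the 6-cycle cut.

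SAP Section 12 states: "There were no substantial changes from the planned analyses described in the protocol version 4.0". It lists two added analysis sets and nothing about the data cut.

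The timing comes from the protocol. Section 6.10.2 fixes DLT evaluability by a 28-day window ("Did not experience a DLT during the 28-day DLT evaluation period"). Section 7.2 sets the cycle length ("A treatment cycle is defined as 28 days for the purposes of scheduling procedures and evaluations"), and Table 7-2 gives the scans as "Q8W to W40 (C3, C5, C7, C9, C11), then Q12W (C14, C17, etc". Dose delays do not move the scans, since "the timing of protocol-specified radiological assessments should be calculated in weeks using C1D1 as reference".

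The counting rules are in SAP Sections 4.3.2, 9 and 9.1.1. Phase I efficacy uses the FAS, which is everyone given any dose. The ORR denominator is every such patient with measurable disease at baseline, each placed in CR, PR, SD, PD or NE. Response needs confirmation at least 4 weeks later (3.5 weeks with the window). SD counts in the DCR only from week 16. No minimum follow-up is set.

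**The concern.** The SAP replaces a data cut that the protocol states outright and then says that nothing substantial changed. That needs correcting whatever its numerical effect.

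The effect is on response rates. The protocol's cut leaves time for two scheduled scans in anyone still on treatment, enough to confirm a response or reach 16-week SD. The SAP's cut can fall before the first scan. A treated patient with measurable disease and no scan fits only NE and remains in the denominator. A patient with a week-8 scan but no later one is also in the denominator and cannot yet be a confirmed responder; SD at week 8 does not count in the DCR. Recently enrolled patients would then pull BOR, ORR and DCR down because of the calendar, not because of the drug. Those patients sit mainly in the last cohort, which is the highest dose in SAP Table 1.

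**Working it through.** **1. Scan calendar.** With 28-day cycles, day 1 of cycle k falls (k − 1) × 4 weeks after C1D1. C3, C5, C7, C9 and C11 fall at weeks 8, 16, 24, 32 and 40; C14 and C17 at weeks 52 and 64. This reproduces the 8-weekly then 12-weekly schedule in Table 7-2.

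**2. Minimum follow-up at each cut.**
- SAP: 28 days = 4 weeks for the last patient. This is a floor, because MTD/RP2D must also have been determined.
- Protocol: 6 × 28 = 168 days = 24 weeks for a patient still on treatment.
- Difference: 168 − 28 = 140 days = 20 weeks.

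**3. What can be observed by then.**
- First scan: day 56, or day 49 if the visit window (plus or minus "7 days (with a minimum of 7 days between doses of IMCnyeso) is allowed") is applied to it. The 4-week floor is 4 weeks short of this, or 3 with the window.
- Earliest confirmed response after a week-8 scan: 56 + 24.5 = 80.5 days = 11.5 weeks. On scheduled scans alone it is week 16.
- Earliest SD that counts in the DCR: week 16.
- At the protocol's cut, scans at weeks 8 and 16 are past due and week 24 is at the boundary.

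**4. How many of cohort 7 are affected.** SAP Table 1 gives 4 + 3 + 5 + 3 + 5 + 4 + 6 = 30 patients, with 6 planned in cohort 7. The documents give no enrolment rate beyond a gap of at least 1 week between the first two patients at a dose level. The gaps below are therefore assumptions, and the cut is placed at day 28 of the last patient.

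| Assumed enrolment of the six | Follow-up of first patient (days) | Reached week 8 | Reached day 80.5 | Reached week 16 |
|---|---|---|---|---|
| First patient 7 days ahead, other five together | 28 + 7 = 35 | 0 of 6 | 0 of 6 | 0 of 6 |
| 7 days apart | 28 + 5 × 7 = 63 | 2 of 6 | 0 of 6 | 0 of 6 |
| 14 days apart | 28 + 5 × 14 = 98 | 4 of 6 | 2 of 6 | 0 of 6 |
| 21 days apart | 28 + 5 × 21 = 133 | 4 of 6 | 3 of 6 | 2 of 6 |
| 28 days apart | 28 + 5 × 28 = 168 | 5 of 6 | 4 of 6 | 3 of 6 |

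**5. Effect on ORR.** Suppose none of the six is assessable, all 30 have measurable disease, and the other 24 have had time for a confirmed response.
- Multiplier: 24/30 = 0.80. A true ORR of 20% has expected value 24 × 0.20 / 30 = 16%; a true 5% becomes 4%.
- Example with exact 95% limits: 3/24 = 12.5% (2.7% to 32.4%) becomes 3/30 = 10.0% (2.1% to 26.5%).
- If, in addition, cohort 7 alone made up the RP2D group, that group would show 0/6 (0% to 45.9%). With full follow-up, the chance of at least one response in six is 1 − 0.80^6 = 74% at a true 20% and 1 − 0.95^6 = 26% at a true 5%.

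**The case against.** The strongest reply has five parts.

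- **No text places a response table in delivery 1.** The SAP does not map outputs to deliveries. In Section 14.2 the BOR tables carry both phases in their titles, which suits delivery 2. The efficacy items labelled Phase I alone are figures (Kaplan-Meier for PFS, OS and DoR; waterfall, swimmer and spider plots), and none reports an ORR. This stands as a condition on the effect. It does not remove the point, since nothing excludes efficacy from delivery 1.
- **The whole last cohort need not be unscanned.** A reader might infer that cohort 7 must show 0/6. The documents do not support that: day 28 is a floor, enrolment is staggered, non-evaluable patients may be replaced, and measurable disease is an inclusion criterion only for Phase II. This stands. Even so, with 14-day gaps no cohort 7 patient has reached the second scheduled scan.
- **The figures cannot steer the RP2D.** A reader might infer that understated activity would feed dose selection. It cannot, because the cut comes after the RP2D is set. Protocol 6.11 opens Phase II on the DLT follow-up of at least 6 patients at that dose, not on this report. This stands in full.
- **PFS and OS are not biased in this way.** Patients without an event are censored, so the loss is follow-up and precision. NE is also tabulated as its own category, so unassessed patients would be visible. Both stand.
- **Later deliveries re-report Phase I, and Protocol 9.1 leaves further reporting detail to the SAP.** The first half stands, although delivery 2 waits on Phase II follow-up and Phase II enrolment is optional. The second half does not excuse the change: a different cut replaces a stated rule and is not added detail.

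**Conclusion.** The point holds with limits. The two cuts contradict each other, no SAP delivery uses the protocol's cut, and Section 12 is wrong to imply that nothing of substance differs. That part rests on the text alone.

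The effect on BOR, ORR and DCR is conditional. It arises only if these are tabulated at delivery 1, and only for patients with measurable disease who were enrolled too recently. Its size ranges from small, with slow staggered enrolment, to a factor of 24/30 on ORR (20% to 16%) under the assumptions in step 5 of the working. It is temporary, because deliveries 2 and 3 supersede it. It does not extend to RP2D selection or to bias in PFS or OS. Nor can it be assumed that the last cohort is the RP2D group: SAP Table 2 allows for cohorts above the RP2D.

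**What to change.** Choose one of two wordings in SAP Section 1:

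- restore the protocol's cut (6 cycles or treatment discontinuation) for the Phase I report; or
- keep the early cut, limit delivery 1 to DLT, safety and PK, and produce Phase I BOR, ORR, DCR, DoR, PFS and OS at the protocol's cut.

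Either way, record the choice in SAP Section 12 and state which Section 14.2 outputs belong to which delivery.

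This changes SAP wording only. The cost of the second option is that Phase I efficacy tables come about 20 weeks after the safety tables. The first option delays the whole Phase I report by about the same time.

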3.6 Definition of End of Study

An individual patient may end participation in the study for reasons listed in [Section 6.19](#).

The planned end of the study occurs when:

- A minimum of 80% of patients have completed the follow-up for disease progression or have discontinued the study for any reason,
- All patients have completed treatment and the Safety Follow-Up Period, and
- The endpoints of best overall response (BOR), OS, progression-free survival (PFS), and duration of response (DoR) have been adequately assessed in all subjects.

Please refer to [Section 9](#) for details of timing of the primary analysis and final reporting of data.

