9.5.2 Phase II: Efficacy

In Phase II, the primary endpoint is the best overall response (BOR). The primary summary measure is ORR, defined as the proportion of patients with a BOR of complete response (CR) or partial response (PR) based on local Investigator assessment, as defined in RECIST v.1.1. ORR will be analyzed separately for the Phase II cohorts. Confirmation of response is required for declaring a PR or CR as the BOR. A confirmed response is defined as a CR or PR followed by a CR or PR at least 4 weeks later. ORR will be summarized with accompanying 95% confidence interval.

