4.1 Sample Size

Dose decisions will be guided by the BLRM. Among the simulations that were conducted, the mean sample size was 27 patients, and the sample size was less than 33 patients in over 80% of simulations.

A Simon two-stage design will be used for each Phase II cohort using a 10% probability of a Type 1 error, a 20% probability of a Type 2 error, and assuming a target response rate of 20% versus 5% response rate for available treatment options. If there are no responses among the first 9 patients in a cohort, then accrual in that cohort will stop. If there is at least one response, at the discretion of the sponsor up to an additional 15 patients may be accrued for a total of up to 24 patients (with at least 3 responses to support further evaluation).

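### The 80% Phase II cut-off sets no minimum follow-up, so up to 4 of 24 patients in a cohort can enter the confirmed ORR as non-responders because it is too early to confirm a response

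*SAP*

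**What the plan says.** - **Cut-off.** SAP Section 1, delivery 2 (the full CSR), uses a "cut-off at the time where at least 80% of phase II patients in each cohort have completed the follow up for disease progression", or have discontinued the study for any reason. Protocol 9.1 has Phase II reported "with a data cut off at the point where at least 80% of patients have completed the follow up for disease progression", with the same alternative of leaving the study but no mention of individual cohorts. Neither adds a condition for patients still ongoing.
- **Endpoint.** Only confirmed responses count: "A confirmed response is defined as a CR or PR followed by a CR or PR at least 4 weeks later" (protocol 9.5.2). SAP 9.1.1 allows a window down to 3.5 weeks.
- **Scans.** Protocol Table 7-2 schedules imaging "Q8W to W40 (C3, C5, C7, C9, C11), then Q12W (C14, C17, etc"), that is at weeks 8, 16, 24 and so on. It contains no separate confirmation scan.
- **Denominator.** The FAS takes anyone dosed (SAP 4.3.2). SAP 9.1.1 puts every FAS or PPS patient with measurable disease at baseline in the ORR denominator and assigns each a BOR of CR, PR, SD, PD or NE. There is no category for patients not yet assessable.
- **Design.** Each cohort follows a Simon two-stage design "assuming a target response rate of 20% versus 5% response rate for available treatment options", "using a 10% probability of a Type 1 error, a 20% probability of a Type 2 error" (SAP 4.1). A cohort stops with no response in 9; at least 3 responses in 24 support further evaluation.
- **Later conditions.** SAP delivery 3 reports again at 100% follow-up. Protocol 3.6 makes it a condition for ending the study that "The endpoints of best overall response (BOR), OS, progression-free survival (PFS), and duration of response (DoR) have been adequately assessed in all subjects".

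**The concern.** The cut-off counts exits, while the endpoint needs time on study. On the schedule, a response first seen at week 8 is confirmed at week 16, and one first seen at week 16 is confirmed at week 24. A patient dosed shortly before the cut has no scan or only one, and is then scored the same as a patient who was fully followed and did not respond.

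This matters most where patients arrive slowly and progress quickly, because the patients still ongoing at the 80% point then tend to be the newest. Slow accrual is plausible: patients must be HLA-A*02:01 positive and antigen positive, and protocol 1.5 puts antigen expression at about 15% in NSCLC and 25% in urothelial carcinoma.

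The plan recognises the need for maturity elsewhere. Protocol 9.1 holds the Phase I report until every Phase I patient has completed 6 cycles or stopped treatment. SAP 9.1.1 does not count stable disease in the DCR before 16 weeks. Phase II, where response is primary, has no such condition at its cut-off. At stake are a downward bias in the ORR of the main report and some loss of power if the 3-of-24 count is read from it.

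**Working it through.** **Inputs from the documents.** n1 = 9, stop at 0 responses; N = 24, at least 3 responses; p0 = 5%, p1 = 20%; error rates 10% and 20% (SAP 4.1); 80% cut-off (SAP Section 1); scans at weeks 8, 16, 24 (Table 7-2).

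**1. Patients who can be outstanding.** 0.8 × 24 = 19.2, so 20 must have finished and 24 − 20 = 4 may be ongoing.

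**2. The plan's own design.** Let X ~ Bin(9, p) be the stage-1 responses and Y ~ Bin(15, p) the stage-2 responses.

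P(at least 3, not stopped) = P(X=1)·P(Y≥2) + P(X=2)·P(Y≥1) + P(X≥3)

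At p = 0.20: 0.302 × 0.833 + 0.302 × 0.965 + 0.262 = 0.252 + 0.291 + 0.262 = 0.805. At p = 0.05 the same sum is 0.093. The stated 80% power and 10% type 1 error are reproduced, with only half a point of power to spare.

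**3. k stage-2 patients too early to confirm.** They add nothing to the count, so Y ~ Bin(15 − k, p). For k = 4 at p = 0.20: 0.302 × 0.678 + 0.302 × 0.914 + 0.262 = 0.205 + 0.276 + 0.262 = 0.743. The expected ORR at a true 20% is 0.20 × (24 − k)/24.

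| k | Power (true 20%) | Type 1 error (true 5%) | Expected ORR (true 20%) |
|---|---|---|---|
| 0 | 80.5% | 9.3% | 20.0% |
| 1 | 79.3% | 8.6% | 19.2% |
| 2 | 77.9% | 7.9% | 18.3% |
| 3 | 76.2% | 7.3% | 17.5% |
| 4 | 74.3% | 6.6% | 16.7% |

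**4. How large k is likely to be.** This needs accrual and PFS, which the documents do not give. The simulations assumed random entry, progression detected at the next scheduled scan, and a cut at the 20th exit or the last first dose, whichever is later. Those giving the power losses below also assumed longer PFS in responders and, in most versions, a pause after stage 1.

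- Accrual 0.5 to 1 per month, non-responder median PFS 1.9 to 3 months: on average 0.9 to 1.9 ongoing patients with under 16 weeks of follow-up at the cut, and a power loss of about 3 to 5 points. All four were immature in about 1% to 4% of runs.
- Accrual of 2 or more per month and median PFS of 4 months or longer: loss under 1 point.
- A harsher model gives every patient the same 2-month median PFS, with no longer-lasting responders, and accrual of 1 to 4 per month. It has all four immature in 8% to 18% of runs. It overstates the problem because ongoing patients who are already confirmed responders are left out.

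**The case against.** The case against giving this much weight is substantial, and most of it stands as a limit on size.

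- **Decision link.** A reader might infer that the 80% cut decides whether a cohort goes forward. The documents do not say so. SAP 4.1 ties the 3 responses to no delivery, SAP Section 4 says no formal hypotheses are tested, and delivery 3 reports at 100% follow-up. Power is lost only if the sponsor acts on delivery 2 and disregards unconfirmed responses, which the listings and swimmer plots would show.
- **Four lost patients.** A reader might take 4 of 24 as the usual case. It is a ceiling: patients still progression-free at the cut may include long-standing confirmed responders.
- **Pooled reading.** Protocol 9.1, read across cohorts, would need 58 of 72 and leave 14 outstanding with no cap per cohort. The SAP states the rule for each cohort, so this larger figure is not supported.
- **Week 16.** This is the earliest confirmation on the scheduled scans, not in principle. An unscheduled scan could confirm at 8 + 3.5 = 11.5 to 8 + 4 = 12 weeks. Nothing bars one; nothing requires one.
- **PPS.** Its second criterion (SAP 4.3.5) removes ongoing patients with no scan. It keeps those with a single unconfirmed response, and the FAS analysis removes neither group.
- **Direction.** The bias lowers both ORR and type 1 error (9.3% to 6.6% at worst), so it cannot create a false positive.

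What remains is that the rule, followed as written, can score a patient as a non-responder for lack of time. Protocol 3.6 does not prevent this, because it governs the end of the study and not the reporting cut.

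**Conclusion.** The point holds as a modest, conservative bias in the primary ORR of the main report. Its size depends on how many ongoing patients lack two scans: 1.2 points of power for one (80.5 − 79.3), up to 6.2 for four (80.5 − 74.3). A loss of about 3 to 5 points rests on assumed slow accrual and short PFS; under faster accrual with longer PFS it is negligible. Because the design has only half a point above 80%, a single such patient takes it below its stated power.

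Delivery 3 can correct the estimate, but only after the main report has presented it, and the SAP leaves open which of the two decides the 3-of-24 count.

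A reader might extend this to the stage-1 rule ("If there are no responses among the first 9 patients in a cohort, then accrual in that cohort will stop"). The 80% cut-off does not govern that count. How long the first 9 patients must be followed is a separate question and is not part of this point.

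**What to change.** 1. In protocol 9.1 and SAP Section 1 (delivery 2), define the Phase II cut-off for a cohort as the later of (a) the 80% point and (b) the date when every treated patient in the cohort has had the week-16 scan, plus the next scheduled scan if a first CR or PR is still unconfirmed, or has progressed, died or left the study.
2. State in the SAP which delivery supplies the ORR for the 3-of-24 decision.

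**Cost.** Wording in two documents, with no extra patients or scans. The main CSR cut may move, at most to about 16 to 24 weeks after the last first dose in the cohort, and not at all where the 80% point already falls later. The change does not wait for responses first seen after week 16; those would still be picked up at 100% follow-up.
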